1.3. Potential Risks and Benefits

To assess any potential impact on subject eligibility with regard to safety, the Investigator must refer to the current version of the tapinarof investigator's brochure for detailed information regarding warnings, precautions, contraindications, AEs, and other significant data pertaining to the study drug being used in this study.

1.3.1. Risk Assessment

1.3.1.1. Dermatological Adverse Events, Including Skin Irritation, or Allergic Reaction:

Tapinarof or its excipients may induce skin irritation. Allergic or irritant reactions in the exposed areas may present as erythema, edema, papules, or vesicles. In the event of pronounced skin reaction, spreading of the eczematous reaction beyond the original application site(s) and/or more generalized (remote) skin reactions may be observed.

In the dose-ranging study (Study 203120) in subjects with psoriasis, the most frequently reported dermatologic AEs were folliculitis and contact dermatitis. In the dose-ranging study (Study 203121) in subjects with atopic dermatitis, the most frequently reported dermatologic AEs were folliculitis and atopic dermatitis. Nonclinical dermal toxicity studies of up to 8% tapinarof for up to 13 weeks indicated local effects are primarily mild-to-moderate skin irritation that is reversible; tapinarof did not show evidence of sensitization. In initial clinical studies using a different formulation of tapinarof AEs of skin hyperpigmentation, application site dermatitis, papular rash, pruritus, contact dermatitis, folliculitis, erythema, and skin burning sensation were reported.

1.3.1.2. Systemic Adverse Events:

Nasopharyngitis and headache were the most frequently reported nondermatological AEs in the dose-ranging study (Study 203120) in subjects with psoriasis. In the dose-ranging study (Study 203121) in subjects with atopic dermatitis, the most frequently reported nondermatological AEs were nasopharyngitis, upper respiratory tract infection, and headache. In the initial clinical studies (in psoriasis and atopic dermatitis) using a different tapinarof formulation, nasopharyngitis, and headache were the most frequently-reported nondermatological AEs. In Study 201851 with of tapinarof cream, 1% and 2%, headache was most frequently reported during the study (reported for 100% and 60% of subjects at the 1% and 2% doses, respectively).

In a nonclinical study in minipigs using IV administration, reversible decreases in arterial blood pressure and PR interval were observed; however, in this study and repeat dermal toxicity studies, there were no effects on QT interval or HR. Repeat-dose dermal toxicity studies also showed findings related to the liver (increased weights and hepatocellular hypertrophy/regeneration) and thymus (thymic cortex depletion in adult rabbits and rats; changes in thymus weight, microscopic decreased cellularity, and changes in thymic T cell maturation in juvenile rats) with associated secondary hematological findings. Thymic findings were also noted in repeat adult and juvenile rat studies; however, there were no clinically relevant AEs/serious adverse events (SAEs) reported.

To mitigate potential systemic risks, subjects will be monitored for AEs and any abnormal vital signs, physical examination, and laboratory test results.

1.3.1.3. Reproductive and Developmental Toxicity

Results of embryo-fetal development studies in rats and rabbits indicated an increased risk for embryo-fetal developmental effects, as evidenced by an increase in post-implantation loss and incidence of fetal skeletal variations. Results of a juvenile rat study indicated adverse microscopic changes in the form of renal pelvic dilatation in both sexes, along with reversible increases in total urinary glucose and protein excretion in males at $\geq 10/15$ mg/kg/day tapinarof (administered subcutaneously).

An investigative study in rats suggested an increased risk for hydronephrosis during a narrow window of postnatal sensitivity prior to postnatal day (PND) 32 (specifically PND 15 to 21). Rat renal tubule anatomic maturation and nephrogenesis occurs during this period [Cappon, 2010; Frazier, 2013; Zoetis, 2003], however tubule morphogenesis/nephrogenesis occurs entirely prenatally in humans [Cappon, 2010; Zoetis, 2003].

To mitigate these potential risks, women of childbearing potential (WOCBP) must utilize abstinence or a highly effective method of contraception consistently and correctly during the study and for 4 weeks after the end of treatment (Section 4.2). Pregnant women and subjects under 18 years of age will be excluded from the study. If a woman becomes pregnant during the study, she will immediately discontinue the study drug. Additionally, AEs will be monitored and clinical laboratory testing will be performed.

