4.2. Inclusion Criteria

Each subject must meet all of the following criteria to be eligible to participate in the study:

- 1. Male and female subjects ages 18 to 75 years with confirmed clinical diagnosis of chronic psoriasis and stable disease for at least 6 months prior to the study;
- 2. BSA involvement ≥ 20% (the subject's scalp, palms, and soles should be excluded from the %BSA calculations to determine eligibility at Screening);
- 3. A PGA score of ≥ 3 at Screening;
- 4. WOCBP and male subjects who are engaging in sexual activity that could lead to pregnancy must use at least 1 of the following adequate birth control methods while on study and for 4 weeks after the last exposure to study drug. Acceptable contraception methods are:
 - Male or male partner with vasectomy, OR
 - Male condom AND partner use of one of the contraceptive options below:
 - Spermicide;
 - Contraceptive subdermal implant that meets effectiveness criteria including a < 1% rate of failure per year, as stated in the product label;
 - Intrauterine device or intrauterine system that meets effectiveness criteria including a < 1% rate of failure per year, as stated in the product label;
 - Oral contraceptive, either combined or progestogen alone;
 - Injectable progestogen;
 - Contraceptive vaginal ring;
 - Percutaneous contraceptive patches.

Note: Subjects using hormonal contraceptives must have been on a stable dose for at least 4 weeks before Baseline.

These allowed methods of contraception are only effective when used consistently, correctly, and in accordance with the product label. The Investigator is responsible for ensuring that subjects understand how to properly use these methods of contraception.

Non-childbearing potential is defined as premenarchal; pre-menopausal females with a documented bilateral tubal ligation, bilateral oophorectomy (removal of the ovaries) or hysterectomy; or hysteroscopic sterilization; or postmenopausal females defined as a cessation of menses for at least 12 months without an alternative medical cause. In questionable cases a blood sample with simultaneous follicle-stimulating hormone

(FSH) > 40 mIU/mL is confirmatory. Documented verbal history from the subject is acceptable.

Subjects who are abstinent are eligible, but they must agree to use one of the birth control methods listed above if they start engaging in sexual activity that could lead to pregnancy during the study.

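### The embryo-fetal risk section relies on highly effective contraception, but the inclusion criterion it cites requires only an adequate method

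*Protocol*

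**What the plan says.** Protocol Section 1.3.1.3 states that animal studies "indicated an increased risk for embryo-fetal developmental effects", naming post-implantation loss and skeletal variations in the fetus. As the first mitigation it says that women of childbearing potential "must utilize abstinence or a highly effective method of contraception consistently and correctly during the study". The requirement is extended by 4 weeks beyond treatment, and the sentence refers to Section 4.2, so that section is named as the place where the safeguard is put into effect.

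In Section 4.2, inclusion criterion 4 says that such women, and male subjects, whose sexual activity could lead to pregnancy "must use at least 1 of the following adequate birth control methods while on study", again with a 4-week tail. There are two routes. One is vasectomy of the male subject or male partner. The other is "Male condom AND partner use of one of the contraceptive options below", followed by seven options: spermicide, subdermal implant, intrauterine device or system, oral contraceptive, injectable progestogen, vaginal ring and patch. Two of these carry an effectiveness condition: "Contraceptive subdermal implant that meets effectiveness criteria including a < 1% rate of failure per year, as stated in the product label" and "Intrauterine device or intrauterine system that meets effectiveness criteria including a < 1% rate of failure per year, as stated in the product label". The synopsis repeats the criterion with the same adjective and the same list.

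**The concern.** A risk section and the criterion it cites should describe the same safeguard. Here they use different standards, and the one that sites apply is the criterion. Section 4.1 treats adherence to the eligibility criteria as essential, and Section 6 rules out waivers except for immediate safety concerns. A site that follows Section 4.2 to the letter is never asked whether a woman's method is highly effective.

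What is at stake is participant protection and the accuracy of the benefit-risk statement. Section 1.3.3 rests its conclusion on the measures taken to reduce risk. An ethics committee that reads Section 1.3 could believe that a stricter requirement is in force than the one written into eligibility. Contraception also carries much of the prevention during dosing: after the Day 1 test, the schedule has no further pregnancy test until follow-up or early termination.

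**Working it through.** No sample size, error rate or estimate is involved, so the check compares the texts.

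**1. The two statements side by side**

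| Element | Section 1.3.1.3 | Section 4.2, criterion 4 (and synopsis) |
|---|---|---|
| Standard named | Highly effective | Adequate |
| Definition of that standard | None; points to Section 4.2 | A list of accepted methods |
| Abstinence | Accepted | Accepted; a listed method is needed if sexual activity that could lead to pregnancy begins |
| Duration | Study plus 4 weeks after treatment ends | Study plus 4 weeks after last exposure |
| Consistent, correct use | Required | Stated as the condition for the methods to work |

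The rows agree on abstinence, duration and correct use. They differ on the effectiveness standard.

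**2. What the list requires**

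- Vasectomy: stands alone, with no threshold stated.
- Condom plus a partner option: seven options. Two carry the below-1% yearly failure condition (implant; intrauterine device or system). That leaves 7 − 2 = 5 with no stated threshold: spermicide, oral, injectable, ring and patch.
- Every one of the seven is used together with a male condom, so none is accepted as a single method.
- Condom plus spermicide meets the criterion with no effectiveness condition on either part.

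**3. Is the gap closed elsewhere?**

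No other section of the protocol or SAP defines highly effective or adds a stricter contraceptive rule. The wording of both passages is intact, so redaction does not explain the difference. The synopsis matches Section 4.2, so the mismatch is not a slip in one copy of the criterion.

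**4. Timing of pregnancy testing**

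Table 1 schedules tests at Screening, Day 1, and follow-up or early termination. For a subject who completes the study, follow-up falls 7 to 10 days after Day 29, that is Day 29 + 7 = 36 to Day 29 + 10 = 39. With last exposure on Day 29, the 4-week contraceptive tail runs to Day 29 + 28 = 57. The tail therefore extends 57 − 39 = 18 to 57 − 36 = 21 days past the last scheduled test.

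**The case against.** The strongest reply is that the two passages need not conflict. Section 1.3.1.3 leaves its term undefined and refers the reader to Section 4.2, so the list there can be taken as what the sponsor meant by highly effective. To say that condom plus spermicide falls outside the term needs a classification from an outside source. This stands to the following extent. A reader might infer that the stated safeguard is not delivered, or that women will be enrolled on methods that fail it. The documents do not support that inference, because they give no definition and no failure rate for any combination.

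A reader might also infer that every woman using an option without the below-1% figure is affected. That does not follow either. The figure qualifies two product types and is not offered as the test for the whole list. Applied as a general test it would also catch vasectomy, which has no figure. The condom requirement weakens the inference further for the hormonal options.

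It is also fair to say that other protections exist: negative tests before dosing, exclusion of pregnant and lactating women, a test at follow-up or early termination, discontinuation on pregnancy, outcome follow-up, and investigator responsibility for explaining correct use. Most of these act before dosing or after a pregnancy has occurred. They limit the consequence of the mismatch but do not remove it.

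What the reply does not answer is the change of adjective. If the list is the intended standard, the risk section describes it with a stronger term than the criterion itself uses.

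**Conclusion.** The point holds as an internal inconsistency on a participant-safety measure. The criterion that Section 1.3.1.3 cites does not require the standard that section names. The gap is clearest for condom plus spermicide, which is accepted with no stated effectiveness threshold.

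Its size cannot be given as a number. The documents do not say how many of the approximately 20 planned subjects will be women of childbearing potential, or which methods they will use. No endpoint, analysis set or estimate is affected.

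The conclusion rests only on the wording of the two sections and the synopsis, and on the absence of any other definition in the protocol or SAP. It takes no position on which contraceptive standard is right. It is more than clerical, because resolving it changes either the eligibility rule or the description of risk mitigation behind the benefit-risk conclusion.

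**What to change.** Reconcile Section 1.3.1.3, inclusion criterion 4 in Section 4.2, and the copy in the synopsis, so that the standard named in the risk section is the one the criterion enforces. Whatever term is kept should be defined once in the protocol and used in all three places. Which standard applies, and so which passage changes, is for the sponsor and the ethics committee.

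The cost is a protocol wording change, submitted to the IRB or IEC as Section 11.2.1 requires. Any consent text that repeats either statement would need the same correction; the consent pages were not available for this review, so whether they do is unknown. Design, sample size and analysis stay as they are.

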1.3.2. Benefit Assessment

Subjects may experience improvements in their psoriasis during the course of the study and may benefit from the additional safety assessments conducted as part of the study (e.g., physical examination, laboratory tests). Subjects in the study will also contribute to the process of developing a novel anti-inflammatory agent for the topical treatment of psoriasis.

1.3.3. Overall Benefit Risk

Taking into account the measures taken to minimize risk to subjects in this study, the potential risks identified in association with tapinarof are justified by the anticipated benefits that may be afforded to subjects with psoriasis.

OBJECTIVES AND ENDPOINTS 2.

The objectives and associated endpoints of the study are as follows:

Objectives	Associated Endpoint
Primary	Primary
To evaluate the safety and tolerability of topical tapinarof cream, 1% in adult subjects with extensive plaque psoriasis	 Frequency and severity of AEs (local and systemic) Laboratory and biomarker values Vital signs ECGs Mean Local Tolerability Scale scores by visit
To evaluate the PK of topical tapinarof cream, 1% in adult subjects with extensive plaque psoriasis	 Tapinarof and tapinarof sulfate (metabolite) plasma PK parameters on Day 1 and Day 29, if data permit, including: AUC_{0-τ} C_{max} t_{max} t_{1/2}
Secondary	Secondary
To exclude clinically relevant effects of tapinarof cream, 1% on QTcF	 Analysis of ΔQTcF at each post-treatment time point on the sampling day with the higher C_{max} (Day 1 or Day 29) Concentration-QTc analysis investigating the relationship between tapinar of plasma concentration and ΔQTcF, if data permit
To assess the efficacy of tapinar of cream, 1% in adult subjects with extensive plaque psoriasis	 Mean change from Baseline to Day 29 in PGA, PASI, and %BSA
Exploratory	Exploratory

3. STUDY DESIGN

3.1. Overall Design

This is a Phase 2a, multicenter, open-label study to evaluate the safety and PK of topical tapinarof cream in adults with extensive plaque psoriasis. The study will consist of three phases: Screening (up to 34 days), Treatment (29 days), and Follow-up (7-10 days).

At Day -1, eligible subjects will be enrolled into the study. During the treatment period beginning on Day 1 (Baseline), subjects will apply tapinarof cream, 1% to affected areas once a day for 29 days. Subjects will return to the clinic on Days 2, 15, 29, and 30 for study assessments and will receive a phone call on Days 8 and 22. Subjects will return to the clinic for a follow-up visit 7-10 days after the Day 29 visit. On clinic visit days, subjects will apply the study drug under the supervision of site personnel, after assessments have been completed. Full PK profiles and Holter monitoring will be collected on Day 1 and Day 29 (with corresponding 24-hour time points collected on Day 2 and Day 30, respectively). Limited PK sampling will be performed on Day 15. Pre-treatment, time-matched Holter monitoring will be conducted on Day -1 and the morning of Day 1.

Study drug will be dispensed to subjects during the clinic visits and will be administered at home between clinic visits as instructed by site personnel. Subjects will be instructed to apply study drug once daily to all affected areas, including newly appearing plaques and plaques/areas that improve during the study. Subjects will apply sufficient study drug to cover completely each lesion with a thin layer of study drug and will record the time of study drug application in a daily diary provided by the study site. Note that subjects are allowed, but not required, to treat palms, fingernails, soles, toenails, and scalp plaques with study drug. If a subject chooses to treat plaques on palms, fingernails, soles, toenails, and/or scalp, they should do so for the entirety of the treatment period from Day 1 to Day 29. Subjects will be instructed to apply study drug in the morning throughout the entirety of their participation in the study. At the phone contacts at Days 8 and 22, subjects should be reminded to complete their daily diary and bring it with them to the next clinic visit.

Study drug application instructions will be reviewed at all post-randomization clinic visits. On clinic visit days, subjects will be instructed/reminded on how to apply study drug (except during the final treatment/end-of-study visits). During the clinic visits, subjects will apply the daily dose of study drug while on-site under the supervision of site personnel, after other assessments have been completed.

Subjects who withdraw from the study before Day 30 will complete an Early Termination Visit. Study duration for subjects who complete this study is approximately 10 weeks in total. Refer to Section 6 for descriptions of study procedures and assessments and Section 7 and the Schedule of Assessments (Table 1) for timing of procedures and assessments.

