Study drug Dispensation / Collection			X			X		X		
Training on drug application			X	X	X	X	X			
Dispense/collect subject diary			X			X		X		
Tapinarof cream administration in- clinic under site supervision			X	X		X		X		
Serial PK profile samples ^e			X	X		X		X	X	
			X	X				X	X	
AE/SAE review	X	X	X	X	X	X	X	X	X	X
Concomitant medication review	X	X	X	X	X	X	X	X	X	X

Note: Phone calls to subjects are on Day 8 and Day 22

Abbreviations: %BSA = percent body surface area; AE = adverse event; BMI = body mass index; BP = blood pressure; ECG = electrocardiogram; ET = early termination; Hep = hepatitis; HIV = human immunodeficiency virus; LTS = local tolerability scale; PGA = Physician Global Assessment; PASI = Psoriasis Area and Severity Index; PK = pharmacokinetic; SAE = serious adverse event; WOCBP = women of childbearing potential

- ^a The subject's scalp, palms, and soles should be excluded from the %BSA calculations.
- b On Day -1, a Holter monitor will be attached for approximately 13 hours to collect pre-treatment, time-matched ECG data. 12-lead ECGs will be extracted from the continuous recording at time points corresponding to time points on Day 1 and Day 29. Subjects will rest in a supine or semi-recumbent position for at least 10 minutes before and 5 minutes after each time point for ECG extraction.
- ^c On Day 1 and Day 29, a Holter monitor will be attached one hour prior to dosing and for 12 hours post-dose. 12-lead ECGs will be extracted at the same time points as PK samples, i.e., pre-dose and at 1, 2, 3, 4, 5, 8, and 12 hours post-dose. Subjects will rest in a supine or semi-recumbent position for at least 10 minutes before and 5 minutes after each time point for ECG extraction. All ECG extractions will be performed immediately before the PK sample is drawn.
- d On Day 2 and Day 30, a Holter monitor will be attached for one hour prior to the 24-hour post-dose PK time point to allow for extraction of 12-lead ECGs corresponding to the 24-hour post-dose PK time point. Subjects will rest in a supine or semi-recumbent position for at least 10 minutes before and 5 minutes after the time point for ECG extraction. The ECG extraction will be performed immediately before the PK sample is drawn.

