1.1.2. Study Rationale

This Phase 2a maximal use study is being conducted as part of a clinical development program to evaluate the safety (including ECG parameters) and systemic exposure of tapinarof cream, 1% for the topical treatment of plaque psoriasis in adults. Maximal use trials enroll subjects with the disease under study and who generally have more severe disease or with a large BSA of affected skin who might be more susceptible to systemic AEs. The purpose of these studies is to evaluate systemic exposure under conditions that would maximize the potential for drug absorption with the intended use of the product [Bashaw, 2014]. The results of this study are intended to support product registration in the United States.

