5.1.5. Administration of Study Drug

Study drug will be dispensed to subjects at the clinical site in appropriately labeled tubes.

Subjects will take the tubes home and self-administer study drug (or have caregiver apply if necessary), except on clinic visit days (when study drug is applied under supervision at the site), to affected areas once daily.

Subjects will be instructed to apply study drug as follows:

- Once daily application to affected areas each morning.
- Study drug should be applied to dry, clean skin.
- Wash hands after application, unless treating plaques on the hands or fingernails.
- Study drug should be applied to all plaques, including newly appearing plaques and plaques that have improved during the study.
- Subjects are allowed, but not required, to treat palms, fingernails, toenails, and scalp plaques with study drug. If using study drug on scalp, no other treatment for scalp psoriasis is permitted during the study. If a subject chooses to treat plaques on palms, fingernails, soles, toenails, and/or scalp, they should do so for the entirety of the treatment period from Day 1 to Day 29.
- If there is residual cream visible on the disease-affected skin, then the subject should be instructed to continue to lightly rub the cream into the skin until it is no longer visible.
- If study drug is applied to the subject by another person, that person should thoroughly wash his/her hands after application. When possible, use of disposable gloves is recommended.
- Subject should record the time of study drug application in the daily diary.
- Subjects should avoid swimming, bathing, showering, or strenuous activities for at least 2 hours after application of study drug.
- On clinic visit days, study drug should be applied in the clinic under the supervision of site personnel and after assessments have been completed.
 - NOTE: The time of the dose and assessments on clinic visit days will depend on the time of the clinic visit (clinic visits should be scheduled for the morning to allow time to complete all study procedures). While the subjects should be instructed to apply study drug in the morning throughout the entirety of their participation in the study, the timing of the clinic visit may lead to a slight deviation from the subject's normal dosing time; if this occurs, it will NOT be considered a protocol deviation; the subject should resume their morning dosing time following any such clinic visit application.

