6.2.2. Body Surface Area Affected

The assessment of the %BSA affected is an estimate of the percentage of total involved skin with psoriasis. For the purpose of clinical estimation, the total palmar surface of the subject's palm (including fingers) may be assumed to be approximately equivalent to 1% BSA. The %BSA affected by psoriasis will be evaluated (from 0 to 100%). Details on calculation of approximate %BSA involvement in each subject (total and individual areas) are provided in Appendix 2. %BSA is a static assessment made without reference to previous scores. Note that plaques on the scalp, palms, and soles should be excluded from the %BSA calculations used to determine eligibility.

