APPENDIX 1. PHYSICIAN GLOBAL ASSESSMENT

Each assessment should be made as a visual 'average' of the severity of all treated areas at the time of the assessment.

Scoring should not be influenced by extent of plaques, participant symptoms, or impact on participant's quality of life.

Score/Grade Description		Description	
0	Clear	No signs of psoriasis; post-inflammatory hyperpigmentation may be present	
1	Almost clear	No thickening; normal to pink coloration; no to minimal focal scaling	
2	Mild	Just detectable to mild thickening; pink to light red coloration; predominantly fine scaling	
3	Moderate	Clearly distinguishable to moderate thickening; dull to bright red, clearly distinguishable erythema; moderate scaling	
4	Severe	Severe thickening with hard edges; bright to deep dark red coloration; severe/coarse scaling covering almost all or all plaques	

APPENDIX 2. CALCULATION OF PERCENT BODY SURFACE AREA AFFECTED AND PSORIASIS AREA AND SEVERITY INDEX

The %BSA affected and PASI will be calculated using the following regional body areas:

- Head and neck
- Trunk, includes internal axillae and groin
- · Upper extremities, includes arms, external axillae, and hands
- Lower extremities, includes legs, buttocks, and feet

Note: At Screening, Baseline and for all efficacy assessments, plaques on scalp, palms, fingernails, toenails, and soles will not be included in the calculation of %BSA affected as these areas will not be included in the efficacy analyses.

Complete the %BSA assessment before the PASI.

Calculation of %BSA Affected:

Measurement of involved BSA is estimated by the handprint method: the total palmar surface of the subject's palm and digits is approximately 1% of their total BSA.

Estimate the involved regional area by determining the number of "full" handprints plus the number of handprints covered if several smaller plaques are "pushed together." Each region can have up to 100% involvement.

- Head and neck = 10% of overall BSA (10 handprints);
 1 hand-sized plaque ~ 10% of head and neck area
- Upper extremities = 20% of overall BSA (20 handprints);
 1 hand-sized plaque ~ 5% of the upper extremities

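### Dosing of scalp, palm, sole and nail plaques is optional in this maximal-use trial, no described procedure records the choice, and the area-normalised PK leaves those sites out of its denominator

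*Protocol*

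**What the plan says.** **Purpose.** Protocol 1.1.2 says that trials of this type "evaluate systemic exposure under conditions that would maximize the potential for drug absorption with the intended use of the product", and that the results are to support US registration.

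**Dosing.** Protocol 5.1.5 gives a general rule: "Study drug should be applied to all plaques, including newly appearing plaques and plaques that have improved during the study". Both 3.1 and 5.1.5 then make an exception. Section 3.1 reads "subjects are allowed, but not required, to treat palms, fingernails, soles, toenails, and scalp plaques with study drug"; 5.1.5 reads "Subjects are allowed, but not required, to treat palms, fingernails, toenails, and scalp plaques with study drug". The 5.1.5 sentence omits soles, although a later sentence in the same bullet includes them. A subject who opts in is to continue from Day 1 to Day 29. SAP 4 repeats the option.

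**Area measurement.** Footnote a of Protocol Table 1 says "The subject's scalp, palms, and soles should be excluded from the %BSA calculations", and Sections 7.3 and 7.8 repeat this for Day 1 and Day 29. Appendix 2 adds the nails: "plaques on scalp, palms, fingernails, toenails, and soles will not be included in the calculation of %BSA affected", and applies this at Screening, Baseline and every efficacy assessment. Section 6.2.2 ties the exclusion only to the eligibility calculation.

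**PK analysis.** SAP 11 summarises Cmax and AUC0-τ by day for the PK analysis set. It also normalises both to the %BSA treated, but defines the divisor as the area of disease in cm², at 185 cm² per 1% BSA.

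**The concern.** A maximal-use trial is read as showing the upper end of exposure. If a subject leaves diseased skin undosed, the measured Cmax and AUC0-τ may fall below what full dosing would have given. If a subject doses the optional sites, the exposure is real but the area it is divided by is too small. The two cases pull different outputs in opposite directions, and the described data do not tell them apart:

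- %BSA leaves the sites out, and the PASI area scores are converted from the same %BSA.
- The diary is described as holding the time of application, not the site.
- SAP 10.7 counts subjects dosing seven sensitive areas, none of them scalp, palms, soles or nails.
- Tube weights are recorded in combination and only listed (Protocol 5.4, SAP 10.2). They give total cream used, not where it went or which plaques were missed.

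PK is a primary endpoint. The QT conclusion in SAP Appendix D is drawn on the day with the higher mean Cmax, so it too depends on exposure having been near maximal.

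**Working it through.** The plan states no figure to reproduce here; the sample size rests on feasibility. The check is area arithmetic.

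**Inputs from the documents**
- Minimum counted area at entry: 20% BSA, excluding scalp, palms and soles (Protocol 4.2).
- Palms: "the total palmar surface of the subject's palm (including fingers) may be assumed to be approximately equivalent to 1% BSA" (Protocol 6.2.2), so both palms are about 2% BSA, or 2 × 185 = 370 cm².
- Head and neck: 10% of BSA (Appendix 2), a ceiling for the scalp.
- Area conversion: 185 cm² per 1% BSA (SAP 11).

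**Assumptions, because the documents give no figure**
- Soles 1-3% BSA and scalp 1-5% BSA. With palms at 2%, fully involved sites total 2 + 1 + 1 = 4% to 2 + 3 + 5 = 10% BSA (740 to 1,850 cm²). Nails are given no area.

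**Formulas.** Let B be counted %BSA and E the involved %BSA on the optional sites.
- Sites left undosed: undosed share of diseased skin = E/(B + E).
- Sites dosed: the reported normalised value is X/(185 × B), while the value per cm² dosed is X/(185 × (B + E)). The ratio is (B + E)/B, so the overstatement is E/B. The 185 cancels.

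**Undosed share, E/(B + E)**

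| E | B = 20% | B = 30% | B = 40% |
|---|---|---|---|
| 2% (palms only) | 2/22 = 9.1% | 2/32 = 6.25% | 2/42 = 4.8% |
| 4% | 4/24 = 16.7% | 4/34 = 11.8% | 4/44 = 9.1% |
| 10% | 10/30 = 33.3% | 10/40 = 25.0% | 10/50 = 20.0% |

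**Overstatement of normalised PK, E/B**

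| E | B = 20% | B = 30% | B = 40% |
|---|---|---|---|
| 2% (palms only) | 10.0% | 6.7% | 5.0% |
| 4% | 20.0% | 13.3% | 10.0% |
| 10% | 50.0% | 33.3% | 25.0% |

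These are per-subject values for full involvement. Both quantities are zero when the optional sites are clear. The first is also zero when the sites are dosed, and the second when they are not. The first equals a shortfall in exposure only if absorption per cm² is the same at every site, which the documents do not state.

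**The case against.** Several points on the other side are sound.

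- **The instructions do not contradict each other.** A reader might infer that dosing all plaques and leaving some optional cannot both stand. But the option is worded as an explicit exception, next to the general rule, in both 3.1 and 5.1.5. The textual defects are smaller: soles missing from one sentence of 5.1.5, and the mismatch between 6.2.2 and Table 1 with Appendix 2.
- **The purpose is qualified.** Section 1.1.2 refers to the product's intended use. If that use leaves these sites optional, optional dosing need not depart from maximal use. The documents do not say.
- **The SAP does more than pool.** It also tabulates area-normalised PK. For subjects who leave the optional sites undosed, the counted area approximates the dosed area, so the normalised figure is about right. It fails for the other group.
- **A record may exist.** The SAP cites an annotated eCRF that is not available here. SAP 10.7 names sites that Protocol 6.3.6 does not, so site-level fields can exist without being described in the protocol. Dosing on both full PK days is supervised in clinic. One can say that no described procedure captures the choice, not that nobody can know it.
- **The larger percentages need a particular subject.** They combine the entry minimum with full involvement of all the sites. Every subject also has at least 20% BSA of other plaques to dose.
- **Measured concentrations are unaffected.** Any concentration-QTc model uses observed plasma levels, not area.

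What remains is that the choice is left open, that no described record shows how it was exercised, and that one planned PK output has a denominator that does not match its label.

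**Conclusion.** The point holds as a gap in data capture and as an error in the normalised PK denominator; it is inexpensive to correct.

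From document figures alone, fully involved palms at 20% counted BSA mean 9.1% of diseased skin undosed, or a 10% overstatement of normalised Cmax and AUC0-τ if they are dosed. With all the sites assumed to total 4-10% BSA and fully involved, the undosed share is 17-33% at 20% counted BSA and 9-20% at 40%. The overstatement is 20-50% at 20%.

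A reader might infer that the trial's mean exposure is understated by 17-33%. The documents do not support that. The figures are conditional, apply to single subjects and have a floor of zero. Nothing says how many subjects have involved optional sites or leave them undosed, and uniform absorption is not established.

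A reader might also want the maximal-use conclusion to rest only on subjects who dosed all involved skin. That would select on completeness, not on exposure. A subject with 45% BSA dosed and one untreated scalp plaque would be dropped, while one with 20% BSA and a clear scalp would be kept. Among about 20 subjects this could lower the reported maximum.

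**What to change.** 1. **Reconcile the text.** The sponsor should reconcile the optional-site wording in Protocol 3.1 and 5.1.5, including the missing soles, with the purpose in 1.1.2. It should also reconcile 6.2.2 with Table 1 and Appendix 2 on whether the %BSA exclusion covers eligibility only or all visits. Which dosing rule should stand is for the sponsor; this review takes no position.
2. **Record the choice.** On Day 1 and Day 29, separately from the efficacy %BSA, record handprints of scalp, palm and sole involvement and a yes/no for each site dosed. If the eCRF already holds these fields, cite them in the SAP.
3. **Correct the denominator.** In SAP 11, divide Cmax and AUC0-τ by the area actually dosed, so that dosed optional sites are counted.
4. **Add one descriptive summary.** Present PK by whether all involved skin was dosed, counting subjects with clear optional sites as fully dosed. Place it beside the pooled primary summary, not in its place.

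The cost is a protocol clarification, a few form fields at existing visits, one revised derivation and one extra table. The subgroups will be small among about 20 subjects and can only be read descriptively.
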